2.4. Study procedures and assessments

Study time points comprise the screening visit to determine eligibility, two baseline visits (the second one includes randomization and treatment initiation after baseline assessments are completed), on-treatment study time points (week 2, 4, 6, and 8 visits), and a final week 14 follow-up visit to assess sustained treatment effects and safety.

Study visits take place at the MGH Translational and Clinical Research Center and the Athinoula A. Martinos Center for Biomedical Imaging. We obtain and manage study data using a web-based secure Research Electronic Data Capture (REDCap) system [38].

See Figure 2 for an overview of the study design, including visits, endpoints, and assessment methods. Table 2 provides a detailed list of study procedures/assessments at each study visit.

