2.3. Study and safety endpoints

The primary endpoint is percent change in body weight from baseline following 8-week intranasal oxytocin compared to placebo. Key secondary endpoints include change from baseline to end of treatment in (a) REE (adjusted for lean mass), (b) body composition (total body, visceral, and liver fat mass), and (c) caloric intake (adjusted for weight) following 8-week intranasal oxytocin compared to placebo.

Other secondary endpoints include change in metabolic profile (e.g., insulin sensitivity, lipid panel, high-sensitivity C-reactive protein [hsCRP] at 8 weeks; fat metabolism at 2 weeks), behavior (e.g., eating behavior, reward-related food motivation, impulse control, social emotional functioning, symptoms of disordered eating, depression, and anxiety), and quality of life between baseline and 8-week intranasal oxytocin treatment compared to placebo (Table 2).

We systematically assess safety and treatment tolerability throughout the study (Table 2), with a final safety visit 6 weeks after treatment completion and additional visits if needed (e.g., early termination). We categorize severity of adverse events according to the Common Terminology Criteria for Adverse Events (CTCAE, v5.0) [37] and evaluate expectedness of adverse events and relationship to study drug and procedures.

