2.5. Biostatistical considerations

2.5.1. Sample size and statistical power

Sixty-one participants were randomized to obtain evaluable data for at least 50 participants completing the 8-week treatment period. We conducted power and sample size calculations using 2-sample t-tests at a 2-tailed significance level of $\alpha = 0.05$. The primary endpoint of this study is percent change in body weight from baseline following 8-week intranasal oxytocin treatment compared to placebo; with 25 participants per arm, we have 80% power to detect a between-group (oxytocin versus placebo) mean difference in weight loss of ≥ 3.2 kg, based on a reported

standard deviation for the between-group difference in weight loss of approximately 4 kg in a pilot study of 8-week intranasal oxytocin administration in adults with obesity [35].

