2.5.3. Statistical analysis plan

Figure 3 shows our statistical analysis plan. We will perform statistical analyses using R statistical software, and appropriate R packages [54]. For continuous endpoints (see 2.3.), we will apply mixed model regression for repeated measurements (MMRM). We will consider the between-group (oxytocin versus placebo) difference in the least-squares mean change of each individual endpoint variable from baseline to each follow-up study time point of interest as the response in MMRM; the change from baseline to week 8 study time point (end of treatment) will be of primary interest (see 2.3.). Treatment group (oxytocin versus placebo), study time point (visit), and treatment group*study time point interaction will be included as fixed factors in MMRM. The baseline value of the endpoint variable and stratification factors (biological sex, BMI) will be entered as covariates. Additional covariates may be considered as appropriate. The intercept and time slope of individual participants will constitute random effects. Parameters of MMRM will be estimated via restricted maximum likelihood (REML). Depending on the distributional characteristics of the data, we may apply logarithmic transformations and/or robust statistical methods. We will adjust for multiple comparisons where appropriate via the approach of Hothorn, Bretz, and Westfall based on single-step simultaneous inference using a joint multivariate t-distribution [55]. We will use a modified intention-to-treat approach for efficacy analyses, including all randomized participants with available data for at least the second baseline visit

(randomization/initiation of treatment) and the first on-treatment study time point. We will apply a per-protocol approach for sensitivity analysis, including only randomized participants who complete the study and demonstrate $\geq 80\%$ adherence to treatment. We will carefully examine patterns of any missing data regarding their relationships with the outcomes of interest and incorporate uncertainty due to missing data with multiple imputations where applicable.

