
 • 18–45 years old • BMI ≥ 30 kg/m² • Willingness to maintain current diet and lifestyle for the duration of study participation (e.g., agree not to start any special diets or lifestyle changes intended to modify weight) 	
Weight/diet
 
 • Weight change >5 kg within 3 months prior to randomization • Nonstandard diet (e.g., Paleo, Atkins, raw diet, macrobiotic diet) • Significant change in physical activity or diet within 1 month of randomization 
Medical/psychiatric conditions
 
 • History of any of the following medical conditions: 
 ○ Cardiovascular disease, prolonged QT on EKG at screening visit ○ Clinically significant gastrointestinal disorder ○ Bariatric surgery (except for participants with a history of laparoscopic adjustable gastric band surgery) ○ Bleeding disorder ○ Untreated thyroid disease ○ Malignancy within 5 years of screening visit (except for basal cell carcinoma or squamous cell carcinoma) ○ Epilepsy ○ Any significant illness or condition that the investigator determines could interfere with study participation and impact data collection or participant safety • History of an eating disorder or psychosis • Current psychiatric disorder (unless on stable dose of anti-depressant or anti-anxiety treatment for ≥ 6 months with no active symptoms that would qualify for an active psychiatric diagnosis as assessed by the Mini-International Neuropsychiatric Interview) • Substance use disorder active within the last 6 months or clinical suspicion of ongoing substance use disorder at screening visit (based on history, Mini-International Neuropsychiatric Interview, and/or lab results) • Current smoking or tobacco use • Allergy to lidocaine 
Medications
 
 • Medication changes within 4 weeks of enrollment • Oral contraceptives • Use of prescription or over-the-counter drugs or dietary/herbal supplements affecting metabolism, blood glucose, or appetite (metformin allowed if on stable dose with stable weight for ≥ 3 months) 
Screening labs
 
 • Hematocrit $>2\%$ below normal • Fasting glucose >125 mg/dL or hemoglobin A1c $\geq 7\%$ • Liver transaminases (ALT, AST) >2.5 times upper limit of normal • Creatinine >1.5 mg/dL • Hyponatremia 
Further exclusion criteria
 
 • Contraindications to MRI and/or DXA • Pregnancy or breastfeeding • Unwilling to use a medically acceptable form of contraception throughout the study period (female of child-bearing potential only) • Participation in any clinical study involving an investigational drug, device, or biologic within 1 month of randomization

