^tReading the Mind in the Eyes Test (behavioral task) assessing theory of mind [75].

^uState Adult Attachment Measure (self-report) capturing attachment insecurity [76].

^vToronto Alexithymia Scale (self-report) measuring the ability to describe and identify emotions [77].

BL, baseline visit; T, Treatment; W, week of visit; HR, heart rate; MMSE, Mini-Mental Status Exam; CBC, complete blood count; TSH, thyroid stimulating hormone; CMP, comprehensive metabolic panel (including liver [alanine/aspartate transaminase] and renal [creatinine] function tests, electrolytes [potassium, sodium], and glucose); HbA1c, hemoglobin A1c; EKG, electrocardiogram; M.I.N.I., Mini-International Neuropsychiatric Interview; hCG, human chorionic gonadotropin; REE, resting energy expenditure; DXA, dual-energy X-ray absorptiometry; MRI, magnetic resonance imaging; 1H-MRS, magnetic resonance spectroscopy; hsCRP, high-sensitivity C-reactive protein; VTA, ventral tegmental area; OFC, orbitofrontal cortex; dlPFC, dorsolateral prefrontal cortex; dACC, dorsal anterior cingulate cortex; preSMA, anterior portion of the supplementary motor cortex; BDI, Beck Depression Inventory; STAI, State Trait Anxiety Inventory; SF-36, 36-Item Short Form Survey.

Table 3. Characteristics of the randomized participants at baseline (BL1 visit).

Characteristic	Mean (SD) or N (%)
Demographics	
N randomized	61
Biological sex: F M	33 (54.10%) 28 (45.90%)
Age (years)	33.58 (6.22)
Race	
• Asian	6 (9.84%)
• Black	13 (21.31%)
• White	38 (62.30%)
• Other/More than one race	3 (4.92%)
• Asked but unknown	1 (1.64%)
Ethnicity	
• Hispanic/Latino ethnic group	12 (19.67%)
Clinical characteristics	
BMI (kg/m ²) [F M]	37.02 (4.93) [37.77 (4.92) 36.13 (4.87)]
BMI distribution (kg/m ²)	
• ≥30 to <35 [F M]	24 (39.34%) [8 16]
• ≥35 to <40 [F M]	21 (34.43%) [15 6]
• ≥40 [F M]	16 (26.23%) [10 6]

Abbreviations: F, female; M, male; BMI, body mass index.

Figures

[figure not shown]

Figure 1. Proposed model of oxytocin effects on eating behavior and metabolism leading to weight loss.

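### Baseline is not tied to a visit: name the BL2 value for weight, and use both baseline records for food intake, where precision can be gained at no cost

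*Combined protocol and SAP*

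**What the plan says.** Section 2.4 describes "two baseline visits (the second one includes randomization and treatment initiation after baseline assessments are completed". Everything recorded at BL1 and BL2 is therefore pre-treatment.

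Table 2 shows what is measured at both visits: anthropometrics including weight (also at screening), the 4-day food record, the 24-hour recall, and the appetite and eating-behavior scales. REE, DXA, abdominal MRI, liver spectroscopy and the test meal have one baseline measurement, at BL1.

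The endpoint and model do not name a visit:
- Section 2.3: "The primary endpoint is percent change in body weight from baseline following 8-week intranasal oxytocin compared to placebo".
- Section 2.5.3: "The baseline value of the endpoint variable and stratification factors (biological sex, BMI) will be entered as covariates".
- Figure 3 writes the contrast as week 8 minus BL, and the abbreviation lists expand BL only as the baseline visit.

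Two places do name one, and they differ. Table 3 is titled "Characteristics of the randomized participants at baseline (BL1 visit". The modified intention-to-treat rule in section 2.5.3 requires data from the second baseline visit, which it identifies with randomization and the start of treatment.

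**The concern.** Two pre-treatment weights exist and the primary endpoint does not say which one is the starting point. If BL1 is used, weight gained or lost before the first dose becomes part of the week-8 change. That adds noise to the primary comparison. Because both weights will be in the dataset, it also leaves an undeclared choice on the primary test.

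For endpoints that vary a lot from one measurement to the next, the stakes differ. A single baseline value is a poor covariate, and a second one has already been collected. The 4-day food record matters most: Table 2 schedules no other intake measure at week 8 (the test meal and the recall are last scheduled at week 6), and Figure 3 lists week-8 caloric intake as a key secondary contrast.

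**Working it through.** **1. The plan's own figure.** Section 2.5.1 states "with 25 participants per arm, we have 80% power to detect a between-group (oxytocin versus placebo) mean difference in weight loss of ≥ 3.2 kg", using a "standard deviation for the between-group difference in weight loss of approximately 4 kg in a pilot study". The standard error is 4 × √(2/25) = 1.131 kg, and 3.2/1.131 = 2.83. With two-sided alpha 0.05, normal-approximation power is Φ(2.83 − 1.96) = 80.7%; the noncentral t gives 79.1%. The stated 80% reproduces. Below, 4 kg is taken as the SD of change from BL2, with t-test power 79.1% as reference.

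**2. Weight: BL1 in place of BL2.** The interval between the visits and the drift over it are not given. Assume a drift SD *d*, independent of later change. The variance becomes 16 + *d*², a relative increase of *d*²/16.

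| Assumed *d* (kg) | Added variance | SD (kg) | Power at 3.2 kg |
|---|---|---|---|
| 0.5 | 0.25/16 = 1.6% | 4.03 | 78.5% |
| 1.0 | 1.00/16 = 6.3% | 4.12 | 76.7% |
| 1.5 | 2.25/16 = 14.1% | 4.27 | 73.7% |

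Simulated covariance analyses of percent change, 25 per arm, agree within simulation error; the highest increase seen was about 16%.

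**3. Bias and error rate.** One simulation assumed weight 105 kg (SD 17), drift mean −0.5 kg (SD 1) and visit noise SD 0.5 kg. Type I error was 5.0% with BL1 and 5.1% with BL2. Under a 3.2 kg effect the mean estimate was −3.14 percentage points for both, with power 74.8% and 77.1%. In similar simulations with that effect, BL1 and BL2 gave different significance results in 5.5%, 7.7% and 11.6% of trials for *d* = 0.5, 1.0 and 1.5 kg. With no effect, taking the smaller p-value raised the error rate from 5% to a little over 6%.

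**4. Weight: BL1 as an additional covariate.** With no drift and visit noise SD *s*, a second baseline weight can save about *s*²/(2 × 16): 0.8% at *s* = 0.5 kg and 3.1% at 1.0 kg. Estimating one more coefficient costs about 1/50 = 2%. The net is about 1% worse to 1% better. Simulation with the stratification covariates gave +1.5%, +0.3% and −0.8% in variance at *s* = 0.5, 0.75 and 1.0 kg. There is no useful gain.

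**5. Food record: one baseline value or two.** Let *r* be the correlation between the two baseline records (assumed 0.4 to 0.7), and *kr* the correlation of either with week 8. Residual variance, as a fraction of the week-8 variance, is 1 − (*kr*)² with one record and 1 − 2(*kr*)²/(1 + *r*) with the mean of two.

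| *k* | *r* = 0.4: one, mean, reduction | *r* = 0.7: one, mean, reduction |
|---|---|---|
| 1.0 | 0.840, 0.771, 8% | 0.510, 0.424, 17% |
| 0.8 | 0.898, 0.854, 5% | 0.686, 0.631, 8% |
| 0.6 | 0.942, 0.918, 3% | 0.824, 0.792, 4% |

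Entering the records as two covariates gives somewhat less in simulation, about 1 to 15%, because of the additional coefficient. The mean is preferable.

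**6. Keeping response and covariate consistent.** The gain requires the change itself to be taken from the mean. If change is taken from BL2 and only the mean is a covariate, (1 − *r*)/2 is added back. At *r* = 0.4 and *k* = 1 that gives 0.771 + 0.300 = 1.071, worse than the 0.840 with one record.

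**The case against.** The strongest reply is that this is one missing sentence. The analysis-set rule requires BL2 data, which favors BL2, and Table 3 is a descriptive table that does not define the endpoint. That stands in part: BL2 is the more natural reading. But requiring data from a visit does not make its weight the baseline, and the only table labeled with a baseline visit names the other one.

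The assumed drift can also be challenged. Table 1 excludes "Weight change >5 kg within 3 months prior to randomization", a limit of about 5/13 = 0.38 kg per week. At that rate a drift of 1.0 or 1.5 kg needs about 2.6 or 3.9 weeks between visits. The upper part of the range is therefore plausible only if the visits are weeks apart.

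The food-record gain has limits too. The 17% requires that baseline records predict week 8 as well as they predict each other. The record is self-reported, and the test meal used in Aim 2 and the mediation analyses has a single baseline, so nothing changes there. This is why the range starts at 3%.

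Two stronger readings are tempting. A reader might infer that pre-drug weight change contaminates the treatment effect. It does not: it precedes randomization and falls on both arms alike. A reader might also infer that the plan discards the second baseline value. The documents do not say so. They use the singular, are silent on how the two visits combine, and allow additional covariates where appropriate.

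**Conclusion.** The concern holds as a matter of precision and specification. The documents do not fix baseline weight for the primary endpoint, and their two cues point to different visits. Any rule set in advance is valid, and BL2 is the more precise of the two visits. Using BL1 would add about 1 to 16% to the variance for an assumed drift SD of 0.5 to 1.5 kg. Leaving the choice open would allow a small inflation of the error rate.

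The more useful gain is in noisy endpoints with two baseline values. For the week-8 food record it is about 3 to 17%. This rests on assumed reliabilities of 0.4 to 0.7, on baseline-to-week-8 correlations of 60 to 100% of the correlation between the baseline records, and on the two records being equally reliable. It does not carry over to weight, where a second covariate gains nothing.

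**What to change.** 1. In sections 2.3 and 2.5.3, state that baseline weight is the pre-dose value at BL2, both as the starting point and denominator of percent change and as the model covariate. Replace BL by BL2 for weight in Figure 3, and label the BL1 data in Table 3 as descriptive.
2. For noisy endpoints measured at both baseline visits, above all the 4-day food record, define baseline as the mean of the BL1 and BL2 values, or the available one if the other is missing. Use this mean both for the change and as the covariate.
3. Do not add BL1 weight to the primary model. Endpoints with one baseline measurement are unaffected.

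The cost is a few sentences, settled before unblinding. No new data are needed, and using a mean adds no model parameter.

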2.4.1. Diagnostic and screening measures

We ask potential participants to complete a pre-screening questionnaire to establish preliminary study eligibility (Table 1). Following informed consent, we confirm eligibility at a screening visit, including review of medical history and physical examination, anthropometric measurements, pregnancy test in females, urine drug screen, blood tests (Table 2), electrocardiogram, and the Mini-International Neuropsychiatric Interview (M.I.N.I.) [39] to evaluate for current/past psychiatric conditions.

2.4.2. Anthropometric measurements

Anthropometric measurements are assessed by trained personnel using calibrated instruments. They include measurements of height (in triplicate using a stadiometer, at screening/baseline visits), weight, and waist/hip circumference (smallest, umbilicus, midpoint, iliac, broadest hip). BMI, waist-to-hip ratio, and percent ideal body weight are calculated (see Table 2 for formulas).

2.4.3. Resting energy expenditure (REE)

We perform indirect calorimetry (VMAX Encore 29 metabolic cart/Viasys Healthcare/Carefusion/San Diego/CA/USA) to assess fasting REE at baseline, week 6 and 8 visits.

2.4.4. Body composition

We obtain body composition measurements at baseline and week 8 visits. We use dual-energy X-ray absorptiometry (Hologic Horizon A/Hologic Inc./Marlborough/MA/USA) to measure total fat mass (precision 3% [40]), total lean mass, estimated visceral adipose tissue mass, and trunk fat mass. On a 3T MRI system (Siemens Trio/Siemens Medical Systems/Erlangen/Germany), we perform single-axial slices through the abdomen at the level of L4 and left mid-thigh to determine fat depots and thigh muscle cross-sectional area. We determine abdominal visceral adipose tissue (VAT) and subcutaneous adipose tissue (SAT) cross-sectional areas (cm²) and their sum, total abdominal adipose tissue (TAT), mid-thigh SAT and muscle area (cm²) using VITRAK software (Merge/eFilm/Milwaukee/WI/USA). We assess liver fat via breath-hold single-voxel 1H-MR spectroscopy (1H-MRS) using a PRESS pulse sequence without water suppression: TE = 30 ms, 8 acquisitions, TR = 1500 ms, 1024 data points, receiver bandwidth 2000 Hz [41] and placing a voxel of 20×20×20 mm (8 mL) within the right and left hepatic lobes avoiding vessels or artifact. We use LCModel software (v6.3 -0K/S. Provencher/Oakville/Ontario/Canada) to fit 1H-MRS data, expressed in lipid-water-ratio.

2.4.5. Fat biopsy

Interventional, musculoskeletal radiologists perform abdominal subcutaneous fat biopsies (2–3 core biopsies) at baseline and week 2 visits under sterile conditions and local lidocaine anesthesia using a 14-gauge Temno biopsy needle (CareFusion/San Diego/CA/USA). Biopsies are immediately transferred to dry ice, ethanol, or formalin solution and stored appropriately until

immunohistochemical and molecular analyses to investigate oxytocin effects on fat metabolism pathways involving white adipocyte “browning”, fatty acid oxidation, and lipolysis.

2.4.6. Caloric intake

A validated breakfast test meal [21] takes place after a minimum 10-hour overnight fast at baseline and week 6 visits (oxytocin administration 20–30 minutes before test meal at week 6 visit). Participants select a meal from a menu created by research dietitians using ProNutra™ software (VioCare/Princeton/NJ/USA). Metabolism and Nutrition Research staff prepare double portions with known nutrient content, and participants have 30 minutes to eat as much as they would like. We quantify caloric intake at test meals (i.e., total calories, carbohydrate/fat/protein content) using ProNutra™ software.

At neuroimaging visits (baseline 2 and week 4, study drug administration held until after study visit), we ask participants to eat a standardized meal (~500 kcal, 60% carbohydrates, 20% fat, 20% protein) over 15 minutes in its entirety to allow for assessment of food motivation neural circuitry and appetite hormones in the fed state [42–44]. Caloric intake is quantified using ProNutra™ software.

Self-report measures of caloric intake include 24-hour food recalls and 4-day food records collected from participants at baseline, on-treatment, and off-treatment follow-up visits. Records are analyzed for total calories, macro- and micronutrients by study dietitians using NDS-R software (Nutrition Coordinating Center/University of Minnesota/Minneapolis/MN/USA).

2.4.7. Laboratory assessments

Blood samples are obtained after a minimum 10-hour overnight fast at approximately 8–9 a.m. at all study visits. Additionally, postprandial blood samples are obtained at neuroimaging visits (baseline 2, week 4) at 30, 60, and 120 minutes after a standardized meal (see 2.4.6.). Whole blood samples are immediately processed as follows: addition of Pefabloc® or aprotinin (for

unstable appetite-regulating hormones only), centrifugation (4 °C, 2800xg, 20 minutes) to separate plasma/serum, dispensed into aliquots (acidification with HCl for unstable appetite-regulating hormones only), and storage at -80 °C until laboratory analysis or immediate measurement (e.g., for glucose and HbA1c). We will report assays and characteristics (detection limits, intra-/inter-assay coefficients of variation) in publications using data from this study. We plan to assess metabolic profile (e.g., insulin sensitivity, lipid panel, hsCRP, appetite-regulating hormones) and gonadal steroids. We collect 24-hour urine (e.g., cortisol) and stool (e.g., microbiome) samples, aliquoted and stored at -80 °C, and hair samples (e.g., cortisol; proximal 2 cm segment of approximately 3 mm diameter taken from posterior vertex position). See Table 2 for details.

